1. PROTOCOL SYNOPSIS

Protocol Number: CC-42344-P1-001

Title: A Phase 1 Study in Healthy Participants to Evaluate the Safety, Tolerability, and Pharmacokinetics of Single-Ascending and Multiple-Ascending Doses of the Influenza A Virus Replication Inhibitor CC-42344

Objectives

Part 1: Single-Ascending Dose

The primary objective of Part 1 is to assess the safety and tolerability of increasing doses of CC-42344 when given as a single oral dose to cohorts of healthy participants. Secondary objectives are to assess the pharmacokinetics (PK) of CC-42344 following a single oral dose and to explore the effect of food on a single oral dose PK in healthy participants.

Part 2: Multiple-Ascending Dose

The primary objective of Part 2 is to assess the safety and tolerability of multiple-ascending doses of CC-42344 when administered orally to cohorts of healthy participants. A secondary objective is to assess the PK of CC-42344 when given as multiple oral doses to cohorts of healthy participants.

Study Design

This is a single-center, randomized, double-blind, placebo-controlled phase 1 study of the influenza A virus replication inhibitor CC-42344 given orally to healthy participants.

Part 1: Participants will be randomly assigned within each cohort to receive a single dose of CC-42344 or placebo. Doses will escalate in sequential dose cohorts. It is planned that 4 cohorts will be dosed with 8 healthy participants per cohort (6 active and 2 placebo in each cohort). Each cohort in Part 1 will include the initial dosing of a sentinel group (1 CC-42344 and 1 placebo) at least 24 hours before dosing the remaining 6 subjects in the cohort (5 CC-42344 and 1 placebo). The remainder of the cohort will only be dosed if, in the opinion of the investigator, there is no significant safety concern identified in the sentinel subjects within the first 24 hours after administration of the dose (CC-42344 or placebo). The following regimens are planned:

- Cohort 1A (N=8): 100 mg CC-42344 or placebo.
- Cohort 1B (N=8): 200 mg CC-42344 or placebo.
- Cohort 1C (N=8): 400 mg CC-42344 or placebo on Days 1 and 9 (food effect).
- Cohort 1D (N=8): 800 mg CC-42344 or placebo.

Cohort 1C will be a two-period sequential food-effect cohort in which participants will receive a single dose of study drug under fasted conditions on Day 1 and a single dose of study drug under fed conditions on Day 9.

After the study was conducted, it was found that the Cohort 1C PK data were not interpretable due to issues with the execution of the assay for plasma CC-42344 levels at the contracted laboratory. Therefore, an additional cohort (Cohort 1C-2) will be enrolled to generate the 400 mg PK and food-effect data. This cohort will comprise 6 participants, all of whom will receive a single 400-mg dose of open-label CC-42344 on Day 1 under fasted conditions and a single 400-mg dose of open-label CC-42344 on Day 9 under fed conditions. The study entry criteria, activities, and assessments will be the same as those described for the main study.

Part 2: Participants will be randomly assigned to receive repeated oral doses of CC-42344 or placebo. Doses will escalate between sequential dose cohorts. It is planned that 3 cohorts will be dosed for 14 days and 2 additional cohorts will be dosed for 5 days, with 8 healthy participants per cohort (6 active and 2 placebo).

The following regimens are planned:

- Cohort 2A (N=8): 50 mg CC-42344 or placebo once daily for 14 days.
- Cohort 2B (N=8): 100 mg CC-42344 or placebo once daily for 14 days.
- Cohort 2C (N=8): 200 mg CC-42344 or placebo once daily for 14 days.
- Cohort 2D (N=8): 400 mg CC-42344 or placebo once daily for 5 days.
- Cohort 2E (N=8): 400 mg CC-42344 or placebo twice daily for 5 days.

Summary of Participant Eligibility Criteria

Inclusion Criteria:

1. Healthy males or healthy, non-pregnant, non-lactating females aged 18 to 55 years.
2. Body weight of at least 50 kg.
3. Body mass index ≥ 18.0 and ≤ 32.0 kg/m². If outside this range, eligible at investigator's discretion.
4. Good state of health (mentally and physically) in the opinion of the investigator as indicated by a comprehensive clinical assessment (detailed medical history and a complete physical examination), electrocardiogram (ECG), vital signs, and laboratory investigations (hematology, clinical chemistry, coagulation, and urinalysis).
5. Willing and able to refrain from alcohol and caffeine from 48 hours before the first dose through study confinement.
6. Negative severe acute respiratory syndrome coronavirus 2 (SARS-CoV-2) test, if required and per site policy.
7. Female participants are eligible to participate if they are not pregnant, not breastfeeding, and at least 1 of the following conditions applies:
 - Not of childbearing potential, defined as surgically sterile (hysterectomy,

bilateral salpingectomy, tubal ligation or bilateral oophorectomy - verbal confirmation through medical history review acceptable) or postmenopausal (no menses for 12 months and confirmed by serum follicle-stimulating hormone (FSH) concentration ≥ 40 mIU/mL).

- Of childbearing potential and agrees to practice true abstinence or agrees to use a highly effective method of contraception consistently from 30 days before Day 1 until at least 30 days after dosing. Highly effective contraception includes hormonal contraception (oral, injected, implanted, or transdermal) plus use of a condom, placement of an intrauterine device or intrauterine system plus use of a condom, or a vasectomized male partner (performed at least 6 months prior) who has been documented to no longer produce sperm - verbal confirmation through medical history review acceptable. Contraception requirements do not apply for participants in an exclusively same-sex relationship. Female participants should not donate eggs for 30 days after their last dose.
8. Male participants must agree to practice true abstinence; be surgically sterilized (performed at least 6 months prior and documented to no longer produce sperm - verbal confirmation through medical history review acceptable); or agree to use a condom plus effective contraception (i.e. established use of hormonal contraception - started at least 30 days before Day 1; or placement of an intrauterine device or intrauterine system) for their female partner, if of childbearing potential, from screening and for at least 90 days after dosing and refrain from donating sperm during this period. Contraception requirements do not apply for participants in an exclusively same-sex relationship. Males with pregnant partners may participate if they agree to use a barrier method of contraception.
 9. Must provide written informed consent before any study procedure is performed.

Exclusion Criteria:

1. Participants who have received any investigational drug in a clinical research study within the previous 30 days before screening or 5 half-lives, whichever is longer.
2. Participants who have received any vaccine within 7 days prior to randomization.
3. Participants who are study site or sponsor employees, or immediate family members of a study site or sponsor employee.
4. History of any drug or alcohol abuse in the past 2 years defined as >21 units of alcohol per week for males and >14 units of alcohol per week for females. Where 1 unit = 360 mL of beer, 150 mL wine, or 45 mL of spirits.
5. Current regular smokers or users of e-cigarettes or nicotine replacement products are excluded. Social smokers who have had 3 or less tobacco- or nicotine-containing

products (including tobacco, e-cigarettes and marijuana) in the 3 months prior to first study drug administration are permitted if willing to abstain from smoking during the confinement period.

6. Females of childbearing potential who are pregnant or lactating or planning to become pregnant during the study (female participants of childbearing potential must have a negative pregnancy test at screening and Day -1). A woman is considered of childbearing potential unless she is permanently sterile (hysterectomy, bilateral salpingectomy, and bilateral oophorectomy - verbal confirmation through medical history review acceptable) or is postmenopausal (had no menses for 12 months without an alternative medical cause and a serum FSH concentration ≥ 40 mIU/L).
7. Participants who do not have suitable veins for multiple venipunctures/cannulation as assessed by the investigator at screening.
8. Clinically significant abnormal biochemistry, hematology, coagulation, or urinalysis as judged by the investigator.
9. Positive alcohol breath test or urine test for drugs of abuse at screening or Day -1.
10. Evidence of renal impairment at screening, as indicated by an estimated creatinine clearance of < 80 mL/min using the Cockcroft-Gault equation.
11. Abnormal liver function tests as indicated by alanine aminotransferase (ALT) > 1.5 x upper limit of normal (ULN), aspartate aminotransferase (AST) > 1.5 x ULN or total bilirubin > 1.5 x ULN. Note: may be repeated once at the discretion of the investigator. Participants with results consistent with Gilbert's syndrome may be enrolled at the discretion of the investigator.
12. Positive test result for hepatitis B, hepatitis C, or human immunodeficiency virus (HIV) at screening.
13. Evidence or history of clinically significant allergic (except for untreated, asymptomatic, seasonal allergies at time of dosing), hematological, endocrine, pulmonary, gastrointestinal, cardiovascular, hepatic, renal, psychiatric, or neurological disease.
14. Acute illness (gastrointestinal, infection [e.g., influenza] or known inflammatory process) at screening or Day -1.
15. Abnormal screening ECG, including QT intervals corrected with Fridericia's formula > 450 msec for males or > 470 msec for females, or participant has any cardiac rhythm other than sinus rhythm that is interpreted by the investigator to be clinically significant.
16. Supine resting bradycardia (pulse heart rate [HR] < 40 bpm) or a supine resting tachycardia (HR > 100 bpm) during vital sign measurements at screening or Day -1. Vital sign measurements may be repeated at the investigator's discretion.

17. Hypertension, defined as a supine resting systolic blood pressure >140 mm Hg or a supine resting diastolic blood pressure >90 mm Hg during vital sign measurements at screening or Day -1. Vital sign measurements may be repeated at the investigator's discretion.
18. Hypotension, defined as a supine resting systolic blood pressure <90 mm Hg or a supine resting diastolic blood pressure <40 mm Hg during vital sign measurements at screening or Day -1. Vital sign measurements may be repeated at the investigator's discretion.
19. Known personal or family history of congenital long QT syndrome or known family history of sudden death.
20. Has donated blood or plasma within 30 days prior to screening or had a loss of whole blood of more than 500 mL within the 30 days prior to screening, or receipt of a blood transfusion within one year prior to screening.
21. Taking, or have taken, any prescribed medication in the 14 days before dosing or over-the-counter drug, including herbal remedies, in the 7 days before dosing. Exceptions are vitamins, minerals, paracetamol, hormone replacement therapy, and hormonal contraception. Additional exceptions may apply on a case-by-case basis if considered not to interfere with the objectives of the study, as agreed by the principal investigator and sponsor's medical monitor.
22. Failure to satisfy the investigator of fitness to participate for any other reason.

Investigational Drug

CC-42344

Study Drug Doses and Route of Administration

CC-42344 or placebo given orally. Study drug will be provided in capsule form. Part 1 will include single-ascending doses of CC-42344 100 mg, 200 mg, 400 mg, and 800 mg. The 400-mg food-effect cohort will receive a second dose on Day 9. Part 2 will include multiple doses of CC-42344 50 mg, 100 mg, and 200 mg once daily (QD) for 14 days, and 400 mg QD and 400 mg BID for 5 days.

Safety Assessments

- Clinical chemistry, hematology, coagulation, and urinalysis.
- Vital signs (blood pressure, heart rate, oral temperature, respiratory rate).
- Electrocardiogram.
- Physical examination.
- Adverse events.

Pharmacokinetic Assessment

Plasma CC-42344 concentration.

Criteria for Dose Escalation

- A Safety Monitoring Committee comprising 3 members will review safety and available PK data prior to dose escalation to the next dose cohort in Parts 1 and 2.
 - For dose escalation to proceed, safety data must be available from a minimum of 7 participants who completed the planned safety assessments up to 48 hours after dosing to ensure that at least 5 participants received active study drug.
 - The following data are required for interim study decisions: adverse events, vital signs, safety laboratory values, and ECGs.
 - Dose escalation will not occur with any of the following:
 - a serious adverse reaction (i.e., a serious adverse event considered at least possibly related to the active drug) in one subject.
 - Grade 3 or higher nonserious adverse reactions (i.e., severe nonserious adverse event considered related to the active drug administration) in two participants in the same cohort, independent of whether they occurred within the same system organ class.
-

Sample Size, Power, and Number of Sites

- No formal sample size calculation was done. Based on experience from similar studies, the target number of participants to be enrolled is appropriate for the assessment of safety and tolerability.
 - In Part 1, 32 healthy participants will be enrolled into 4 cohorts, each with 8 participants. An additional 6 participants will be enrolled into an open-label cohort to repeat the Part 1 PK and food-effect investigation with 400 mg.
 - In Part 2, 24 healthy participants will be enrolled into 3 cohorts, each with 8 participants.
 - In both Parts 1 and 2, up to 2 replacement participants may be enrolled per cohort. Participants withdrawn due to an adverse event related to CC-42344 will be considered evaluable and will not be replaced.
 - Planned number of sites: one (Australia).
-

Statistical Analysis

Safety will be assessed based on the actual treatment received for all participants who have received study drug. Data will be summarized using descriptive statistics (number of participants, arithmetic mean, standard deviation, median, minimum, and maximum) for continuous variables and frequency and percentages for categorical variables. In addition, for pharmacokinetic data, the geometric mean and geometric coefficient of variation will be

calculated. Where confidence intervals are presented, they will be two-sided 95% confidence intervals.

Sponsor: Cocrystal Pharma Australia Pty Ltd.

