Additional dose cohort(s) may be added if all previous dosages are well tolerated and accumulated PK and safety data support the addition of higher dose(s).

Part 2: Multiple-Ascending Dose

Part 2 of the study may be opened after satisfactory review of the safety and PK data from the first dose in Cohort 1C.

Participants will be randomly assigned to receive once-daily oral doses of CC-42344 or placebo for 14 days. Doses will escalate between sequential dose cohorts. It is planned that up to 3 cohorts will be dosed with 8 healthy participants per cohort (6 active and 2 placebo).

The following regimens are planned:

- Cohort 2A: 50 mg CC-42344 or placebo once daily for 14 days.
- Cohort 2B: 100 mg CC-42344 or placebo once daily for 14 days.
- Cohort 2C: 200 mg CC-42344 or placebo once daily for 14 days.
- Cohort 2D: 400 mg CC-42344 or placebo once daily for 5 days.
- Cohort 2E: 400 mg CC-42344 or placebo twice daily for 5 days.

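### The synopsis sets Part 2 enrolment at 24 participants in 3 cohorts, but the current five-cohort design enrols 40.

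*Combined protocol and SAP*

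**What the plan says.** The Protocol Synopsis, under Sample Size, Power, and Number of Sites, gives the Part 2 enrolment: "In Part 2, 24 healthy participants will be enrolled into 3 cohorts, each with 8 participants". The line before it covers Part 1: "In Part 1, 32 healthy participants will be enrolled into 4 cohorts, each with 8 participants", plus 6 participants in the open-label repeat of the 400 mg food-effect cohort. Up to 2 replacements per cohort are allowed for in a separate statement.

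The same synopsis, under Study Design, says of Part 2: "It is planned that 3 cohorts will be dosed for 14 days and 2 additional cohorts will be dosed for 5 days", with 8 participants per cohort split 6 active to 2 placebo. Its list gives N=8 for each of 2A to 2E, including "Cohort 2D (N=8): 400 mg CC-42344 or placebo once daily for 5 days" and "Cohort 2E (N=8): 400 mg CC-42344 or placebo twice daily for 5 days".

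Section 6.1 repeats the smaller count for Part 2: "It is planned that up to 3 cohorts will be dosed with 8 healthy participants per cohort". The sentences introducing that count describe Part 2 dosing as once daily for 14 days. The list directly beneath names five cohorts, of which two are dosed for 5 days and one of those two is dosed twice daily.

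Section 11.1 says that no formal sample size calculation was done and gives no number for either part.

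**The concern.** Two passages of current text in one synopsis give different sizes for Part 2, and Section 6.1 contradicts its own list in the same way. With no formal calculation behind the study, the planned count is the whole of the sample-size specification, and the 24 is the only Part 2 sum that is printed.

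What is at stake is the number of healthy volunteers to be exposed, as an ethics committee or monitor would read it. Sections 12.1 and 12.2.2 make the protocol and its amendments subject to ethics committee approval. The 16 participants missing from the count belong to 2D and 2E, which have the highest daily doses among the multiple-dose cohorts. Enrolment carried out as designed would exceed the number stated for Part 2.

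**Working it through.** No power formula applies, so the check is a direct count.

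**Inputs**
- Part 2 as stated: 3 cohorts of 8 (Synopsis, sample size).
- Part 2 as designed: 3 cohorts for 14 days plus 2 for 5 days, 8 per cohort, 6 active and 2 placebo (Synopsis, Study Design).
- Part 1: 4 cohorts of 8, plus 6 in Cohort 1C-2 (Synopsis, sample size).
- Replacements: up to 2 per cohort (Synopsis, sample size; Section 7.2.3).

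**Step 1. Reproduce the stated figure.** 3 × 8 = 24. The sentence is correct on its own terms, so the multiplication is not at fault.

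**Step 2. Count the current design.** Cohorts: 3 + 2 = 5. Participants: 5 × 8 = 40. Active: 5 × 6 = 30. Placebo: 5 × 2 = 10.

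**Step 3. Size of the gap.** 40 − 24 = 16, and 16 / 40 = 40%. The gap equals Cohorts 2D and 2E: 2 × 8 = 16, of whom 2 × 6 = 12 are active and 2 × 2 = 4 placebo.

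**Step 4. Sum over both parts.** As stated: 32 + 6 + 24 = 62. As designed: 32 + 6 + 40 = 78. The difference is again 16. Both totals are sums made here.

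**Step 5. With maximum replacements in Part 2.** As stated: 3 × (8 + 2) = 30. As designed: 5 × (8 + 2) = 50.

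**Step 6. Is five cohorts the current design?** 2D and 2E appear in these places:
- the synopsis dose summary;
- their own schedule of events (Section 2.4);
- the Section 6.1 list;
- the dose rationale (Section 6.2);
- Table 2 (Section 8.3.1);
- the administration instructions (Section 8.4);
- the adverse-event window (Section 11.2.7).

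Only the synopsis attaches N=8 to each cohort by name; the Section 6.1 list and Table 2 confirm the cohorts but give no participant numbers for each. Section 14.1 records that Version 5.0 added 2D and 2E, which explains how the count came to be out of date. The contradiction itself lies between passages of current text and does not depend on the change log.

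**Step 7. Can another reading give 24?** Replacements are counted separately and take three cohorts only to 30. 2D and 2E are listed among the planned regimens, so they are not optional. The sentence allowing further dose cohorts stands under Part 1 of Section 6.1, ahead of the Part 2 heading.

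**The case against.** The strongest case on the other side is that this is an editorial leftover with little practical effect. The synopsis list fixes enrolment cohort by cohort, so anyone can count to 40. No analysis, estimate or safety threshold uses the total: dose escalation is decided per cohort, on a minimum of 7 participants (Section 9.4). There is no power, error rate or precision target to be disturbed.

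Most of that stands, and it limits the point. It does not make 24 right. The sample-size part of the synopsis was brought up to date for the 6 participants of Cohort 1C-2, so it is meant to follow amendments, and the Part 2 line was missed.

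Three stronger readings are tempting and are not supported:
- A reader might infer that enrolment would stop after 2C. That is implausible, since 2D and 2E have a full schedule, dose rationale, capsule counts and administration instructions.
- A reader might say that the protocol misstates its overall trial size. The documents print no overall total; 62 is only the sum of the separate statements.
- A reader might take the 24 to be the only enrolment information for Part 2. It is the only printed sum, but the N=8 entries in the same synopsis also determine enrolment.

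**Conclusion.** The point holds as an internal contradiction in a stated sample size. Part 2 is given as 24 where the current design gives 40, a shortfall of 16. The conclusion rests on 2D and 2E being planned cohorts of 8, which the synopsis states outright, and it needs no outside figure. The effect is confined to planned enrolment: the statistical properties of the study do not change. It should be corrected before the document is relied on, because an approved enrolment number ought to match the design and the repair is very cheap.

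**What to change.** 1. In the synopsis sample-size statement, give Part 2 as 40 participants in 5 cohorts of 8 (30 CC-42344, 10 placebo).
2. In Section 6.1, change the Part 2 cohort count from up to three to five.
3. In Section 6.1, reconcile the sentence describing once-daily dosing for 14 days with the cohort list directly beneath it, which includes other durations and a twice-daily cohort.

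Section 11.1 gives no number for either part, so nothing there is wrong; repeating the figure there would be a matter of preference. The cost is a few sentences, with no participants or procedures beyond those the design already lists.

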2. SCHEDULE OF EVENTS

2.1. Part 1: Single-Ascending Dose Schedule of Events

	Screening	Clinical Unit						End of Study Visit ¹⁰
	Day -28 to -1	Day -1	Day 1			Day 2	Day 3	Day 8
Assessments			Pre-dose	Dosing	Post-dose			(+/-1 d)
Unit Check-in		X						
Informed consent	X							
Inclusion/exclusion criteria	X	X	X					
Demographic data	X							
Medical history	X	X	X					
Prior medication history	X	X						
Vein assessment	X							
Physical examination ¹	X	X			X (abbrev)		X (abbrev)	X (abbrev)
Height	X							
Weight	X	X						
12-lead ECG ²	X	X	X		X	X	X	X
Vital signs ³	X	X	X		X	X	X	X
Randomization			X					
Study Drug				X				
Adverse event reporting ⁴				X	X	X	X	X
Concomitant medications			X			X	X	X
Alcohol breath test ¹¹	X	X						
Drugs of abuse screen	X	X						
Pregnancy screen ⁵	X	X						X
FSH ⁶	X							
Serology ⁷	X							
Clinical Safety Labs ⁸	X	X			X	X		X
Plasma CC-42344 levels ⁹			X		X	X	X	
Discharge from Unit							X	

Footnotes

- 1 Physical examination will include examination of general appearance, head, ears, eyes, nose, throat, neck (including thyroid), skin, cardiovascular system, respiratory system, gastrointestinal system, musculoskeletal system, lymph nodes, and nervous system. Abbreviated exam will include at a minimum assessment of general appearance, head, nose, throat, respiratory system, and cardiovascular system.
- 2 Electrocardiogram will be taken in triplicate (a least 1 minute apart and with all 3 completed within 5 minutes) with 12-lead ECG once during screening, on Day -1, on Day 1 pre-dose (within 2 hours) and 2 and 4 hours \pm 10 minutes after dosing, and on Days 2, 3, and 8. ECGs will be measured prior to vital sign measurements with participants in a supine position after a minimum 5-minute rest.
- 3 Vital signs include blood pressure, heart rate, respiratory rate, and oral temperature and will be collected prior to blood draws following a minimum 5-minute rest in a supine position. Vital signs will be measured at screening, on Day -1, on Day 1 prior to dosing (within 2 hours) and 2 and 4 hours \pm 10 minutes after dosing, and on Days 2, 3, and 8.
- 4 Adverse event reporting will be continuous through end of study on Day 8.
- 5 Females of childbearing potential will be screened for pregnancy. The screening pregnancy test will be by blood sample to detect the presence of β -hCG (collected as part of clinical chemistry sample). On Day -1 and at end of study, pregnancy will be determined by urine dipstick.
- 6 Only for women of postmenopausal status.
- 7 Serology screening will include tests for hepatitis B surface antigen, hepatitis C virus, and human immunodeficiency virus.
- 8 Standard clinical safety labs will be collected non-fasted.
- 9 PK samples to be collected before dosing (within 30 minutes) and at 0.25, 0.5, 0.75, 1, 1.5, 2, 2.5, 3, 3.5, 4, 6, 8, 12, 24, 36, and 48 h after dosing. Additional samples to be collected at 72 and 96 hours postdose for Cohorts 1C and 1D. Sampling windows are \pm 5 minutes for samples through 4 h postdose, \pm 10 minutes for samples at 6 and 8 h, \pm 30 minutes for samples from 12 to 48 h, and \pm 4 h for samples at 72 and 96 h. When ECGs and vital signs are scheduled at the same time as PK samples, the sample will be taken at the scheduled time point, with the ECGs and vital signs obtained as close as possible prior to the blood draw.
- 10 End of study visit for all cohorts except for the food-effect cohort, Cohort 1C. See Section 2.2 for schedule of events for days 8-16 for Cohort 1C.
- 11 Alcohol breath testing may be replaced with a question asking that participants confirm that they have refrained from any alcohol intake for the time period outlined in the protocol

2.2. Part 1 Cohort 1C Schedule of Events – Period 2

	Clinical Unit						EOS Visit ⁹
	Day 8	Day 9			Day 10	Day 11	Day 16
Assessments		Pre-dose	Dosing	Post-dose			(+/-1 d)
Unit Check-in	X						
Informed consent							
Inclusion/exclusion criteria	X	X					
Demographic data							
Medical history							
Prior medication history							
Vein assessment							
Physical examination ¹	X			X (abbrev)		X (abbrev)	X (abbrev)
Height							
Weight	X						
12-lead ECG ²	X	X		X	X	X	X
Vital signs ³	X	X		X	X	X	X
High-fat breakfast ⁴		X					
Study Drug			X				
Adverse event reporting ⁵	X	X	X	X	X	X	X
Concomitant medications	X	X			X	X	X
Alcohol breath test ¹⁰	X						
Drugs of abuse screen	X						
Pregnancy screen ⁶	X						X
Clinical Safety Labs ⁷	X			X	X		X
Plasma CC-42344 levels ⁸		X		X	X	X	
Discharge from Unit						X	

Footnotes

Note: The washout window between Period 1 and Period 2 may be optionally extended for up to 3 days, with other Period 2 visits adjusted accordingly. Thus, dosing for Period 2 may occur between Day 9 and Day 12.

- 1 Physical examination will include examination of general appearance, head, ears, eyes, nose, throat, neck (including thyroid), skin, cardiovascular system, respiratory system, gastrointestinal system, musculoskeletal system, lymph nodes, and nervous system. Abbreviated exam will include at a minimum assessment of general appearance, head, nose, throat, respiratory system, and cardiovascular system.
- 12 Electrocardiogram will be taken in triplicate (at least 1 minute apart and with all 3 completed within 5 minutes) with 12-lead ECG on Day 8, on Day 9 pre-dose (within 2 hours) and 2 and 4 hours after dosing ± 10 minutes, and on Days 10, 11, and 16. ECGs will be measured prior to vital sign measurements with participants in a supine position after a minimum 5-minute rest.
- 13 Vital signs include blood pressure, heart rate, respiratory rate, and oral temperature and will be collected prior to blood draws following a minimum 5-minute rest in a supine position. Vital signs will be measured on Day 8, on Day 9 prior to dosing (within 2 hours) and 2 and 4 hours ± 10 minutes after dosing, and on Days 10, 11, and 16.
- 14 High-fat breakfast started and finished within 30 minutes prior to dosing.
- 15 Adverse event reporting will be continuous to end of study on Day 16.
- 16 On Day 8 and at end of study, pregnancy will be determined by urine dipstick.
- 17 Standard clinical safety labs will be collected non-fasted.
- 18 PK samples to be collected before dosing (within 1 hour) and at 0.25, 0.5, 0.75, 1, 1.5, 2, 2.5, 3, 3.5, 4, 6, 8, 12, 24, 36, 48, 72, and 96 h after dosing. Sampling windows are ± 5 minutes for samples through 4 h postdose, ± 10 minutes for samples at 6 and 8 h, ± 30 minutes for samples at 12 to 48 h, and ± 4 h for samples at 72 and 96 h. When ECGs and vital signs are scheduled at the same time as PK samples, the sample will be taken at the scheduled time point, with the ECGs and vital signs obtained as close as possible prior to the blood draw.
- 19 End of study visit.
- 20 Alcohol breath testing may be replaced with a question asking that participants confirm that they have refrained from any alcohol intake for the time period outlined in the protocol

